6.3.1.2.12 Reporting Serious Adverse Events

All SAEs (regardless of their relationship to the study vaccine) should be reported to the CRO Safety Department immediately (i.e., within 24 hours) after the study site's first knowledge of the event. The contact information for SAE reporting can be found in the Investigator site file for the study.

Initial reports of SAEs will be entered in the eCRF and SAE eCRF. If the eCRF is not working for any reason, then SAEs should be reported using the paper SAE report form and submitted using the contact details in the Investigator site file for the study. When additional follow-up information becomes available, a follow-up SAE report (depending on the qualified event) must be completed by the Investigator or a qualified sub-Investigator as soon as possible. The Investigator is responsible for obtaining relevant detailed information to support all SAE reports, including records of inpatient and outpatient care, laboratory reports, and autopsy or medical examiner reports.

6.3.1.2.13 Regulatory Reporting Requirements for Serious Adverse Events Including Suspected Unexpected Serious Adverse Reactions

The Sponsor is required to notify national regulatory agencies and (in conjunction with the Investigator) local regulatory authorities about the safety of a study vaccine under clinical investigation. The Sponsor will comply with country-specific regulatory requirements relating to safety reporting to the regulatory authority, Institutional Review Board (IRB)/Independent Ethics Committee (IEC), and Investigators.

The Sponsor or designee will promptly evaluate all SUSARs against cumulative product experience to identify and expeditiously communicate possible new safety findings to Investigators, applicable IRBs/IECs, and health authorities based on applicable legislation.

To determine reporting requirements for SUSAR cases, the Sponsor or designee will assess the expectedness of these events using the reference safety information contained in the IB.

An Investigator who receives an Investigator safety report describing an SAE or other specific safety information from the Sponsor or designee will review and then file it as appropriate and will notify the IRB/IEC, if appropriate according to local requirements.

6.3.1.2.14 Follow-Up of Participants Reporting Adverse Events

All AEs/SAEs must be reported in detail on the appropriate page on the eCRF and followed to satisfactory resolution, until the Investigator deems the event to be chronic or not clinically significant (NCS), the event is considered to be stable, or the participant is lost to follow-up.

6.3.1.2.15 Reporting Cases of COVID-19 or Asymptomatic SARS-CoV-2 Infection

All participants will be reminded to contact the site within 24 hours for any signs or symptoms of COVID-19 as well as any known exposure to SARS-CoV-2/COVID-19 (see also Section 6.7). For those participants who terminate the study early, participants are requested to continue to report these events to the site and as soon as possible for up to 12 months since the last study vaccine administration.

Any site that is made aware of a case of suspected COVID-19 or asymptomatic SARS-CoV-2 infection must be report this to the Sponsor or designee within 24 hours of Investigator notification.

For participants who describe symptoms of or exposure to COVID-19, the site will complete a dedicated eCRF. For participants who terminate early from the study without withdrawing consent, this information will be captured on a paper case report form (CRF) (located in the Investigator Site File), which should be emailed or faxed to the Sponsor or designee.

The reporting instructions, including the email address or fax number for submitting paper forms, can be found in the Investigator Site File for the study.

All events of COVID-19 will be reviewed by the Sponsor/designee to determine if the case definition of severe COVID-19 ([Appendix 7](#)) is met.

6.3.1.2.16 Laboratory Test Abnormalities

Clinically significant abnormal laboratory test results, in the opinion of the Investigator, may constitute or be associated with an AE. Examples of these include abnormal laboratory results that are associated with symptoms or require treatment, e.g., bleeding due to thrombocytopenia, tetany due to hypocalcemia, or cardiac arrhythmias due to hyperkalemia. Whenever possible, the underlying diagnosis should be listed in preference to abnormal laboratory values as AEs. Severity grading of abnormal test results should follow the grading of unsolicited AEs when the event is deemed clinically significant by the Investigator (Section [6.3.1.2.9](#)). Clinically significant abnormalities will be monitored by the Investigator until the parameter returns to its baseline value or until agreement is reached between the Investigator and Sponsor Medical Monitor (or designee) that further follow-up is not required. Laboratory abnormalities deemed NCS by the Investigator should not be reported as AEs. Similarly, laboratory abnormalities reported as AEs by the Investigator should not be deemed NCS on the laboratory sheet. Where relevant, safety laboratory assessments will be analyzed by toxicity grade at the time of interim and final analysis.

The Investigator is responsible for reviewing and signing all laboratory reports. The signed clinical laboratory reports will serve as source documents and should include the Investigator's assessment of clinical significance of out of range/abnormal laboratory values.

A list of laboratory analytes to be tested is included in [Appendix 3](#).

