1.7 Risk Benefit Assessment

1.7.1 Potential Risks

The potential benefits and risks of ARCT-165/ARCT-154 are informed by the non-clinical and clinical studies conducted with ARCT-021 and non-clinical pharmacology studies conducted with ARCT-165 and ARCT-154. Detailed information about the potential benefits and risks and reasonably expected AEs of ARCT-021, ARCT-154, and ARCT-165 is provided in the IB ([Arcturus 2022a](#)). A summary of the potential risks of treatment with ARCT-021, ARCT-154, and ARCT-165, together with potential mitigation for these risks, is shown in [Table 1](#). As of protocol Version 3.0, the ongoing review of safety data from the ARCT-154-01 and ARCT-021-04 had not identified any confirmed new risks with use of the ARCT-154 and ARCT-165 vaccines. However, hypertension is being evaluated as a signal based on blinded safety data from the ARCT-154-01 study.

Table 1 Risk Minimization Measures Included in Clinical Studies of ARCT-021, ARCT-154, and ARCT-165

Risk	Mitigation

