6.3.1.2.9 Assessment of Severity

Solicited AEs: The intensity of solicited AEs will be graded for severity as Grade 0, Grade 1 (mild), Grade 2 (moderate), Grade 3 (severe), or Grade 4 (potentially life threatening). The severity of solicited AEs will be assessed according to scales based on the US FDA toxicity grading scales for vaccine clinical studies, as shown in [Appendix 5](#).

Unsolicited AEs: The severity of unsolicited AE will be rated as mild, moderate, or severe using the following criteria:

Mild:

- These events require minimal or no treatment and do not interfere with the participant's daily activities.

OR

- An event usually transient in nature and generally not interfering with normal activities.

Moderate:

- These events result in a low level of inconvenience or concern with the therapeutic measures. Moderate events may cause some interference with normal functioning.

OR

- An AE that is sufficiently discomforting to interfere with normal activities.

Severe:

- These events interrupt a participant's usual daily activities and may require systemic drug therapy or other treatment. Severe events are usually incapacitating.

OR

- An AE that is incapacitating and prevents normal activities.

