6.5 Vital Signs and Body Temperature

VS and body temperature will be evaluated for clinical significance. Any clinically significant change in VS or body temperature should be evaluated for an underlying cause and the associated AE reported. If no known cause is determined, the clinically significantly abnormal parameter may be reported as an AE. Severity grading of clinically significant abnormal VS should follow the grading of unsolicited AEs when the event is deemed clinically significant by the Investigator (Section [6.3.1.2.9](#)). All collected VS will also be analyzed by toxicity grade at the time of interim and final analyses.

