7.5.3 Safety Analysis

Safety, reactogenicity, and safety laboratory assessments will be evaluated in the Safety set. Participants will be summarized according to the study vaccine that was received.

Descriptive statistics will be provided for each solicited AE and for each study vaccine group. Local and systemic AEs from Day 1 through Day 7 after each vaccination will be presented by severity cumulatively using a 5-point toxicity grading scale (Grades 0 through 4). Descriptive summary statistics will include counts and percentages of participants with the indicated endpoint.

Descriptive statistics will also be provided for abnormal hematology and chemistry laboratory values at Day 1 and at 3, 7 and 28 days following each dose of the study vaccine, including shifts in toxicity grading (DHHS 2007). Descriptive summary statistics will include counts and percentages of participants with the indicated endpoint.

Unsolicited AEs (including MAAEs, SAEs, and AEs leading to discontinuation/withdrawal) will be categorized according to MedDRA terms. Descriptive summary statistics (counts, percentages) will be provided for any unsolicited AE event in each study vaccine group.

Missing solicited AE diary data will not be imputed; missing AE dates will be handled according to the rules defined in the SAP.

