The number of participants reporting SAEs, MAAEs, AESIs, AEs leading to discontinuation/withdrawal of vaccination, or AEs leading to death will also be presented.

Summaries of unsolicited AEs that are displayed by system organ class and preferred terms will be ordered by descending incidence of system organ class and preferred term within each system organ class for the 154-01 study vaccine group. Summaries displayed by preferred term only will be ordered by descending incidence of preferred term for the 154-01 study vaccine group.

Summaries of the following types will be presented:

- Summary of solicited AEs within 7 days post each vaccination
- Summary of solicited AEs within 7 days post each vaccination by toxicity grade and day
- Summary of solicited AEs within 7 days post each vaccination by toxicity grade
- Summary of duration (days) of solicited AEs post each vaccination
- Overall summary of unique unsolicited AEs and participant incidence of AEs meeting various criteria, including (but not limited to), AESIs, AEs leading to discontinuation, SAEs, and deaths, within 28 days of each vaccine administration;
- Most frequently-occurring ($\geq 10\%$ Overall) unsolicited AEs within 28 days of each vaccination by preferred term
- Participant incidence of unsolicited AEs up to 28 days post each vaccination by MedDRA system organ class and preferred term;
- Participant incidence of unsolicited AEs up to 28 days post each vaccination by severity, MedDRA system organ class, and preferred term;
- Participant incidence of unsolicited AEs up to 28 days post each vaccination by relationship to study vaccine, MedDRA system organ class, and preferred term;
- Participant incidence of unsolicited AEs up to 28 days post each vaccination by relationship to study procedure, MedDRA system organ class, and preferred term;
- Overall summary of unique unsolicited AEs and participant incidence of AEs meeting various criteria, including (but not limited to), AESIs, MAAEs, AEs leading to discontinuation, SAEs, and deaths through end of study;
- Most frequently-occurring ($\geq 10\%$ Overall) unsolicited AEs through end of study by preferred term
- Participant incidence of unsolicited AEs post each vaccination through end of study by MedDRA system organ class and preferred term;

- Participant incidence of unsolicited AEs post each vaccination through end of study by severity, MedDRA system organ class and preferred term;

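### Laboratory and vital-sign AEs are graded by functional impact, and the SAP omits the toxicity-grade summaries that would show how large the abnormality was

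*Protocol*

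**What the plan says.** Protocol 6.3.1.2.16 covers laboratory abnormalities that the investigator considers clinically significant: "Severity grading of abnormal test results should follow the grading of unsolicited AEs when the event is deemed clinically significant by the Investigator". Section 6.5 has the matching rule for vital signs: "Severity grading of clinically significant abnormal VS should follow the grading of unsolicited AEs when the event is deemed clinically significant by the Investigator". Both refer to 6.3.1.2.9.

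That section defines three levels by effect on activity and need for treatment. One alternative for Mild is "These events require minimal or no treatment and do not interfere with the participant's daily activities". One alternative for Severe is "An AE that is incapacitating and prevents normal activities"; the other is an event that breaks into usual activities, may need treatment and is usually, not always, incapacitating. No level has a numeric cut-off.

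These severities feed primary endpoint 1b and SAP 4.6.2, which lists "Participant incidence of unsolicited AEs up to 28 days post each vaccination by severity, MedDRA system organ class, and preferred term" and a similar table through end of study.

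The protocol also commits to a value-based analysis: laboratory results by toxicity grade where relevant (6.3.1.2.16), all collected vital signs by toxicity grade (6.5), and hematology and chemistry summaries "including shifts in toxicity grading (DHHS 2007") in 7.5.3. SAP 4.6.4 instead plans descriptive statistics and low/normal/high shift tables. SAP 4.6.5.1 plans descriptive statistics for vital signs. SAP 4.10 reports no change to the planned analyses.

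**The concern.** A laboratory value or blood pressure can be far out of range without the participant noticing. On a functional scale such a finding tends to fall in the lower categories, because the scale does not ask how large the abnormality was. A reader of the by-severity table who sees no Severe laboratory or blood-pressure AEs may take that as evidence of tolerability, when part of the explanation may be the scale.

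This matters for blood pressure in particular. Protocol 1.7.1 says that "hypertension is being evaluated as a signal based on blinded safety data from the ARCT-154-01 study", and Table 1 of the protocol relies on repeated blood-pressure measurement to detect elevations. The protocol's own counterweight is the toxicity-grade analysis of the values. If the SAP does not carry it out, no planned summary table grades these findings by size.

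**Working it through.** The plan gives no figure to reproduce: Protocol 7.1 and SAP 4.9 report no sample-size calculation, and the study is descriptive. The check is mainly a comparison of text.

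**Step 1. Which scale applies.** Protocol 6.3.1.2.16 and 6.5 both send clinically significant findings to 6.3.1.2.9.

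**Step 2. Where a large, silent finding falls on it.**
- No treatment and no effect on activity: the first alternative for Mild fits.
- Treated, activity unaffected: Moderate can fit, since it refers to concern with therapeutic measures.
- Severe: both alternatives turn on activity. It is reached if evaluation, treatment or admission interrupts the participant's usual day.

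So Mild or Moderate is the ordinary result and Severe is possible.

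**Step 3. How other measured findings are treated.** Appendix 5 grades fever by temperature (39.0–40 °C is Grade 3) and erythema by diameter (more than 10 cm is Grade 3). Section 6.3.1.2.9 labels Grade 3 severe. The protocol thus accepts size-based grading for measured solicited events. Appendix 5 has no laboratory or vital-sign table.

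**Step 4. Whether size is shown elsewhere.**

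| Data | Protocol | SAP |
|---|---|---|
| Laboratory | Toxicity grade and grade shifts (6.3.1.2.16, 7.5.3) | Descriptive statistics; 3×3 low/normal/high shift to worst value (4.6.4) |
| Vital signs | Toxicity grade (6.5) | Descriptive statistics and change from baseline (4.6.5.1) |
| Declared change | – | None (4.10) |

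A low/normal/high table does not separate a value just above the limit from one far above it. Group means of blood pressure do not isolate one participant's extreme reading.

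**Step 5. What one participant is worth.** Planned group sizes follow from Protocol 3.1: A1 12/3 = 4 per group; A2 24 × 3/4 = 18 and 24 × 1/4 = 6; Cohort B 36/3 = 12 per group. Moving one participant into or out of Severe changes the percentage by 100/n:
- A1, n = 4: 25.0 points
- A2 ARCT-021, n = 6: 16.7 points
- Cohort B, n = 12: 8.3 points
- A2 ARCT-154, n = 18: 5.6 points

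In a Cohort B group the exact (Clopper-Pearson) 95% interval is 0 to 26.5% for 0/12 and 0.2% to 38.5% for 1/12.

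**Step 6. How often it might arise.** The documents give no rate of silent, high-grade abnormalities. Assuming a per-participant rate p and independence, the chance of at least one is 1 − (1 − p)^n:

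| Assumed p | n = 12 | n = 72 |
|---|---|---|
| 1% | 11% | 52% |
| 2% | 22% | 77% |
| 5% | 46% | 98% |
| 10% | 72% | more than 99% |

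These rates are illustrative only.

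**The case against.** The strongest reply is that the protocol deliberately uses two axes: the investigator rates clinical impact, and the values are analysed separately by toxicity grade. Nothing requires the two ratings to agree, so a finding that is high-grade on one and Mild on the other is not a contradiction. That stands, and it is why the investigator's severity should be kept. But it defends the protocol, not the SAP, which leaves the second axis out.

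A reader might infer that a silent abnormality can never be Severe, whatever its size. The text does not support this. Treatment or admission can interrupt usual activities, and the first alternative for Severe is only usually incapacitating. A reader might also infer that events are undercounted. They are not: a clinically significant finding reported as an AE is counted whatever its severity.

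Other displays limit the harm. Unscheduled follow-up of an abnormal laboratory result counts as a medically attended AE (Protocol 6.3.1.2.3), and the SAP tabulates these and SAEs. Abnormal laboratory values are listed, and hypertensive crisis has its own entry in Protocol 4.2.2.1. Section 6.3.1.2.16 also prefers a diagnosis to an abnormal value as the AE term where possible, which narrows the affected set. All of this stands. None of these displays, however, summarises the findings by graded size.

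Finally, the 100/n figures apply to any single event in groups this small. They show the table's sensitivity, not a measured bias.

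**Conclusion.** The point holds as a gap in presentation. The functional scale will ordinarily place large but silent laboratory and blood-pressure findings in Mild or Moderate, and the SAP drops, without declaring it, the value-based grading that the protocol sets beside that scale. An absence of Severe AEs of this kind could therefore partly reflect the scale.

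The size cannot be derived from the documents. It depends on how often such findings occur, which is not stated. If one participant's category is at issue, the Severe percentage differs by 5.6 to 25.0 points according to group, assuming planned enrolment and that all are dosed.

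A further inference would be that toxicity grade should replace the investigator's severity. The documents do not settle that in its favour. Protocol 7.5.3 cites DHHS 2007 only for hematology and chemistry, 6.5 names no scale for vital signs, and regrading would also touch the individual rule on severe related unsolicited AEs in 4.2.2.1. Displaying both ratings is a worthwhile, low-cost improvement that avoids those difficulties.

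**What to change.** 1. In SAP 4.6.2, keep the investigator's severity. For unsolicited AEs that are laboratory or vital-sign findings, show the toxicity grade of the associated measurement beside it. Use DHHS 2007 for laboratory values, as Protocol 7.5.3 does. The sponsor should name the scale for vital signs.
2. In SAP 4.6.4 and 4.6.5.1, add the toxicity-grade summaries promised in Protocol 6.3.1.2.16, 6.5 and 7.5.3, including the laboratory grade shifts.
3. The sponsor should reconcile the word Severe in Protocol 4.2.2.1 with 6.3.1.2.9, 6.3.1.2.16 and 6.5, stating which rating it refers to. No clinical rule is proposed here.

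The cost is SAP wording, a derived grade from values already collected, and a modest exercise linking AE terms to those values, which the documents do not currently describe. Some high-grade but clinically minor values will be displayed; the investigator's severity beside them gives the reader the context.

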6.4 Physical Examinations

Any clinically significant change in physical examination should be evaluated for underlying cause and the associated AE reported. If no known cause is determined, the clinically significantly abnormal parameter may be reported as an AE.

6.5 Vital Signs and Body Temperature

VS and body temperature will be evaluated for clinical significance. Any clinically significant change in VS or body temperature should be evaluated for an underlying cause and the associated AE reported. If no known cause is determined, the clinically significantly abnormal parameter may be reported as an AE. Severity grading of clinically significant abnormal VS should follow the grading of unsolicited AEs when the event is deemed clinically significant by the Investigator (Section [6.3.1.2.9](#)). All collected VS will also be analyzed by toxicity grade at the time of interim and final analyses.

6.6 Pregnancy

If a participant becomes pregnant or a pregnancy is suspected, or if a male participant believes his sexual partner has become pregnant during the study participation, the study site staff must be informed immediately. The pregnancy should be reported within 24 hours using a Pregnancy Notification Form and collected in the safety database. The Pregnancy Notification Form should

be sent to the CRO Safety Department. Follow-up information, including delivery or termination, should be reported within 24 hours of study site staff awareness. The contact information for pregnancy reporting can be found in the Investigator Site File for the study.

Female participants: If a suspected pregnancy occurs while on the study in a female participant who has received the study vaccine, a pregnancy test will be performed. If the pregnancy test is positive, the participant will be encouraged to complete all study procedures except receipt of additional doses of the study vaccine (2-dose schedule). Regardless of continued study participation, the study physician will assist the participant in getting obstetrical care and the progress of the pregnancy will be followed until the outcome of the pregnancy is known (i.e., delivery, elective termination, or spontaneous abortion). The study vaccine assignment of the participant may be unblinded according to the judgment of the Investigator, provided unblinding informs a decision relating to pursuit of additional care or vaccination. If the pregnancy results in the birth of a child, the study site and Sponsor may require access to the mother and infant's medical records to obtain additional information relevant to the pregnancy progress and outcome. A longer follow-up may be required if a newborn child experiences a medical condition. Follow-up will be performed to the extent permitted by the applicable regulations and privacy considerations, e.g., a pregnancy ICF may be required.

Male participants: If the female partner of a male participant who has received the study vaccine becomes pregnant, the progress of the pregnancy of the male participant's partner should be followed until the outcome of the pregnancy is known (i.e., delivery, elective termination, or spontaneous abortion). If the pregnancy results in the birth of a child, the study site and Sponsor may follow up with the mother and may request access to the mother and infant's medical records to obtain additional information relevant to the pregnancy progress and outcome. A longer follow-up may be required if a newborn child experiences a medical condition. Follow-up will be performed to the extent permitted by the applicable regulations and privacy considerations, e.g., partner ICF may be required.

